10.7.2 Treatment-Emergent Adverse Events (TEAE)

The treatment emergent period will be defined in two ways:

(1) **TEAEs over a 24-week treatment period** will be defined as AEs that occur, having been absent before the date and time of the first dose of the IMP, or have worsened in severity or seriousness after initiating the IMP until Week 28 (Week 24 + 30 days) in the **24-week treatment period**.

For patients enrolled under protocol versions 1.0 to 4.0, the AEs that occur, or have worsened in severity or seriousness after Week 28 (Week 24 + 30 days) will NOT be taken into consideration in TEAEs over a 24-week treatment period.

(2) TEAEs over a 52-week treatment period will be defined as AEs that occur, having been absent before the date and time of the first dose of the IMP, or have worsened in severity or seriousness after initiating the IMP until Week 56 (Week 52 + 30 days) in the **52-week treatment period**.

For patients enrolled under protocol versions 1.0 to 4.0 who entered the extension phase, the AEs that occur, or have worsened in severity or seriousness after Week 56 (Week 52 + 30 days) will NOT be taken into consideration in TEAEs over a 52-week treatment period.

TEAEs will be assigned to the Extension Phase based on AE start date:

Version Date: 27-June-2024

Sponsor: Calliditas Therapeutics Suisse SA

Protocol No: GSN000350

 If the start date of the TEAE is on or after the first dose in the Extension Phase, the TEAE will be assigned to the Extension Phase.

10.7.3 TEAE Leading to Discontinuation of Study

A TEAE will be classified as a TEAE leading to discontinuation of the study if the answer to the question "Did the adverse event cause the subject to be discontinued from the study?" is Yes on the AE CRF page.

10.7.4 TEAE leading to IMP Withdrawal

A TEAE will be classified as

• a TEAE leading to study drug withdrawal if the answer to the question "Action Taken with Study Treatment" on the AE CRF page is "Drug Withdrawn" or "Unknown".

and/or

• a TEAE leading to treatment discontinuation if the answer to question "Reason for Discontinuation" on the End of Treatment CRF page is "Adverse Event".

10.7.5 TEAEs Related to IMP

A TEAE will be classified as related to IMP if the relationship to study treatment is indicated as Related on the AE CRF page. Additionally, if the relationship is missing, then the TEAE will be deemed related.

10.7.6 Duration of AEs

Duration of AEs will be calculated as AE end date – AE start date + 1. AE duration will only be calculated when complete dates for the start and stop date are provided.

10.7.7 AESIs

An AE will be classified as an AESI is the question "Is this event of special interest?" is marked as Yes on the CRF.

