### 4.2 Exclusion Criteria

A patient who meets any of the following exclusion criteria will not be eligible for inclusion in the study:

- 1. A positive pregnancy test or breastfeeding for female patients.
- 2. Any historical or current hepatic decompensation event defined as variceal/portal hypertension bleed and/or hepatic encephalopathy, spontaneous bacterial peritonitis, ascites requiring treatment, or liver transplantation list inclusion.
- History of liver transplantation, current placement on a liver transplant list or current MELD score of ≥12 unless the patient is on anticoagulant therapy, or a Child-Pugh Score of ≥6.
- 4. Cirrhosis with complications, including history or presence of hepatocellular carcinoma.
- 5. Total bilirubin >2×ULN. In case of total bilirubin elevation >ULN the Screening serum albumin must be within the reference range.

One repeat blood sampling (with analysis by the central laboratory) can be performed at the discretion of the Investigator at Screening Visit 2 for patients who meet this exclusion criterion at Screening Visit 1. If this exclusion criterion is not met at Screening Visit 2, the patient may be eligible for the study.

6. Plasma ALT >3×ULN and/or AST >3×ULN.

One repeat blood sampling (with analysis by the central laboratory) can be performed at the discretion of the Investigator at Screening Visit 2 for patients who meet this exclusion criterion at Screening Visit 1. If this exclusion criterion is not met at Screening Visit 2, the patient may be eligible for the study. 7. INR >1.2 unless patient is on anticoagulant therapy.

One repeat blood sampling (with analysis by the central laboratory) can be performed at the discretion of the Investigator at Screening Visit 2 for patients who meet this exclusion criterion at Screening Visit 1. If this exclusion criterion is not met at Screening Visit 2, the patient may be eligible for the study.

- 8. Estimated glomerular filtration rate (eGFR) <30 mL/min/1.73 m^2, as calculated by the central laboratory using the chronic kidney disease epidemiology collaboration (CKD-EPI) equation.
- 9. TSH >ULN at Screening.

One repeat blood sampling (with analysis by the central laboratory) can be performed at the discretion of the Investigator at Screening Visit 2 for patients who meet this exclusion criterion at Screening Visit 1. If this exclusion criterion is not met at Screening Visit 2, the patient may be eligible for the study.

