#### 5.3.2.1 Suspected Drug-induced Liver Injury

During the study, the Investigator will remain vigilant for increases in liver biochemistry. The Investigator is responsible for determining whether the patient meets DILI criteria at any point during the study.

In the event that a patient has any of the following laboratory results, please refer to Appendix II for details regarding the detection and management of suspected or confirmed cases of DILI, including instructions for retesting, close monitoring, and action to take regarding the IMP:

- AST or ALT  $\geq 3 \times ULN$
- AST or ALT  $>2 \times$  Baseline
- Total bilirubin >2×ULN
- INR >1.5 (except for patients on anticoagulant therapy).

Baseline values for liver tests (ALT and AST) are determined by averaging the values obtained at Screening and Baseline/Day 1 to determine the arithmetic mean.

Details of the IMP stopping criteria relating to suspected or confirmed DILI are provided in Section 4.4 and Appendix II.

Any suspected or confirmed DILI events meeting the criteria for an AESI, as defined in Section 7.1.5, will be reported to the Sponsor (or designee) following the same procedure as for SAEs (see Section 7.4).

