#### 7.1.5 Adverse Events of Special Interest

The AESIs for this study are DILI, anemia, and hypothyroidism.

AESIs of DILI will be defined as any DILI event that meets the criteria in **A**, **B**, or **C** of Appendix II. Please refer to Section 5.3.2.1 and Appendix II for details regarding the detection and management of cases of DILI.

AESIs of anemia will be defined as CTCAE Grade  $\geq 2$  anemia AND absolute reticulocyte counts of <50% of the Baseline value, which is confirmed by repeat testing. Please refer to Section 5.3.2.2 for details regarding the detection and management of potential cases of bone marrow toxicity.

AESIs of hypothyroidism will be defined as TSH levels of  $\geq 10$  mIU/L, which is confirmed by repeat testing at the central laboratory (ie, TSH  $\geq 10$  mIU/L and reduced free T4). Please refer to Section 5.3.2.3 for details regarding the detection and management of hypothyroidism. The AESI should be reported by the investigative site to the ICON Drug Safety Center within 24 hours of learning about the event by completing the paper safety report form and sending it via email or fax. The documentation and processing of AESIs is further detailed in the Investigator Site File.

The AESIs will be adjudicated by the Adjudication Committee (see Section 9.4.1).

Investigators will indicate on the relevant Adverse Event eCRF page if the event meets the criteria for an AESI. If the event meets the criteria for an AESI, the Investigator will inform the Sponsor (or designee) of the AESI utilizing the safety report form (refer to the SAE contact information at the beginning of this protocol) and will then complete the Adjudication Event eCRF.

Please refer to the Investigator adjudication manual for further information.

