10.0 Conventions and Derivations

10.1 Baseline and Change from Baseline

10.1.1 Baseline Values for Liver Biochemistry

Baseline values for liver biochemistry (ALP, ALT, AST, total and direct bilirubin, and GGT) are determined by the geometric mean of the last (up to) 3 measurements preceding the first administration of study drug. This includes unscheduled and screening visits. The formula for the geometric mean (GM) given three measurements a, b, and c is expressed as follows:

$$GM = \exp(\log(a) + \log(b) + \log(c)/3)$$

For subjects who have records for both Screening/Visit 1 and Baseline Visit 3, the baseline will be calculated as the geometric mean of these two values. If there is an additional unscheduled pre-dose result, the geometric mean will be calculated using up to three values.

For subjects who have records for Screening/Visit 1, Screening/Visit 2, and Baseline Visit 3, the Screening/Visit 1 result should be disregarded due to the subject's re-screening. The baseline should be calculated as the geometric mean of the Screening/Visit 2 and Baseline Visit 3 results. If there is an additional unscheduled pre-dose result, the geometric mean should include up to three values.

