For all other assessments (including all other liver function tests captured in Table 8 [serum fibrinogen, albumin, hsCRP and IgM]), the value closest to the target day will be selected for use in the analysis. If more than one assessment is equidistant from the target day, the assessment later in time will be selected. If there is more than 1 record on the selected day, the arithmetic mean of the continuous assessments will be applied, or the worst assessment (for categorical parameters) will be selected. If there is an EoT assessment and a scheduled assessment within a time point, the scheduled assessment should always be selected for use in the analysis. For analysis for determination of worst case values, for example shift tables to the worst post-baseline value, all post-baseline values collected during the time period defined by the analysis set, including unscheduled visits, will be considered.

Table 1a: Analysis Windows for Main Part

Analysis Visit	Target Study Day	Lower Limit	Upper Limit
Baseline	1		1 (pre-dose)
Day 1	1 (post-dose)		
Week 2	15	2	22
Week 4	29	23	43
Week 8	57	44	71
Week 12	85	72	127
Week 24	169	128	183
Week 28 - EOT	196	184	225

Table 2b: Analysis Windows for Main Part for ADQS domains (PROMIS-Short Form Fatigue 7b Daily, PBC-40, PROMIS-29, EQ5L, PGIC, PGIS and WI-NRS)

Analysis Visit	Target Study Day	Lower Limit	Upper Limit
Baseline	1		1 (pre-dose)
Day 1	1 (post-dose)		
Week 4	29	2	71
Week 12	85	72	127
Week 24	169	128	183
Week 28 - EOT	196	184	225

Table 3: Analysis Windows for data collected under protocol versions 1.0 to 4.0, including Extension Phase (EP)

Analysis Visit	Target EP Study Day	Lower Limit	Upper Limit
Week 36	253	226	309
Week 52	365	310	460

Sponsor: Calliditas Therapeutics Suisse SA

Protocol No: GSN000350

Extension Baseline	1		1 (pre-dose in Extension)*
Week 68/Week 16 Extension	113	2	155
Week 80/Week 28 Extension	197	156	239
Week 92/Week 40 Extension	281	240	323
Week 104/Week 52 Extension	365	324	407

^{*}for subjects on Placebo in the Main Part. Study day is relative to first dose in the Extension Phase.

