12.6.3 Laboratory Data

Laboratory data will be reported in Système International (SI) units.

Version Date: 27-June-2024

Sponsor: Calliditas Therapeutics Suisse SA

Protocol No: GSN000350

For clinical biochemistry, hematology and liver function tests (Table 8), shift tables from baseline to worst CTCAE grade on treatment will be produced for the SS, with separate summaries for each treatment period. Only parameters which have toxicity grading will be summarized. WBC and reticulocyte

counts will be expressed in absolute values. Differential count will be expressed as both absolute count and percentage of WBCs. Only central lab data will be included in the table summaries. All lab data collected locally and centrally will be listed.

Table 8: Laboratory Tests

Laboratory Tests	Parameters
Hematology	Hematocrit; hemoglobin; absolute and relative reticulocyte counts, red blood cell (RBC) count; white blood cell (WBC) count; differential WBC count; platelet count; absolute neutrophil count; mean cell volume, INR
Biochemistry	Glucose; total protein; creatinine; urea; total cholesterol; triglycerides; sodium; potassium; chloride
Liver Function	Serum fibrinogen, albumin, ALP, ALT, AST, total and conjugated bilirubin, GGT, hsCRP, lgM

To further examine the liver function tests collected during the study, suspected drug-induced liver injury (sDILI) summaries will be produced. Proportion of subjects meeting any of the following criteria for any post-baseline assessments will be presented for the SS, for each treatment period:

- AST or ALT ≥3xULN
- AST or ALT >2xBaseline
- Total bilirubin >2xULN
- INR>1.5

Any subjects with any of the above criteria for sDILI or cholestasis will be flagged in the listings. Subjects at risk of a drug induced liver injury according to Hy's law will also be flagged. Hepatic function abnormality defined by an increase in AST and/or ALT to \geq 3xULN concurrent with an increase in total bilirubin to \geq 2xULN but without increase in ALP (i.e., ALP < 2xULN) meets the criteria for Hy's law and raises the concern for DILI.

The MELD score will be calculated by the central laboratory based on the results from the liver biochemistry (total bilirubin), biochemistry (creatinine), and hematology (INR) blood samples. Subjects with a MELD score of \geq 15 will be flagged in the listings.

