Data from the Extension Phase will be restricted to the period while a subject was on active and change from baseline comparisons using the extension baseline.

Table 9: Other Laboratory Tests

Laboratory Tests	Parameters
Markers of Liver Fibrosis	ELF score components for calculation of ELF score (TIMP-1, PIIINP, and hyaluronic acid) and the other PBC-related biomarkers (PRO-C3 and C3M; PRO-C3/CRM ratio)
Markers of bile acid metabolism	Total bile acids, C4, FGF19, FGF21
Autoantibodies	AMA titer, PBC-specific antibodies (anti-GP210, anti-SP100, antibodies against major M2 components [PDC-e2, 2-oxo-glutaric acid dehydrogenase complex])

Sponsor: Calliditas Therapeutics Suisse SA

Protocol No: GSN000350

Laboratory Tests	Parameters	
Viral Serology	HIV antibodies (1 and 2) and, if positive for HIV antibodies, HIV RNA; Hepatitis B surface antigen and hepatitis C virus antibodies and, if positive for HCV antibody, HCV RNA	
Pregnancy test	Serum pregnancy test; urine Pregnancy test	
Thyroid function	TSH and free T4	
Drug Screen (Urine)	Urine drug screen	
Urinalysis	pH; protein; glucose; ketones; bilirubin; blood; microscopic examination of the sediment	

Refer to Table 98, for a list of other laboratory parameters to be collected on this study and the laboratory test category each parameter will be summarized under. Autoantibodies, viral serology, pregnancy test, and drug screen parameters will be listed only. Markers of liver fibrosis, markers of bile acid metabolism, urinalysis, thyroid function will be summarized descriptively by scheduled visit using the SS.

Standard ranges from the central laboratory will be used for the laboratory analysis. The assessment as to if a lab test is low, high, normal as applicable will be derived using the standard ranges for central lab data. Laboratory data outside study-specific reference ranges will be listed.

Abnormal laboratory values, defined as values outside the normal range, will be listed by subject. Summaries of the incidence and frequency by treatment group and scheduled visit will be presented.

12.6.4 eDISH Analysis

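### The suspected-DILI table's INR row drops the protocol's anticoagulant exception; laboratory flags for the anemia and hypothyroidism AESIs would be a cheap further check

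*SAP*

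**What the plan says.** **INR criterion.** SAP 12.6.3 introduces the sDILI table with "Proportion of subjects meeting any of the following criteria for any post-baseline assessments will be presented for the SS", for each treatment period. The four rows are AST or ALT at or above 3×ULN, AST or ALT above 2×Baseline, total bilirubin above 2×ULN, and INR above 1.5. The INR row has no qualifier. The same criteria drive a flag in the laboratory listings. Protocol 5.3.2.1 and Appendix II list the same four laboratory triggers but exempt patients on anticoagulant therapy from the INR one. Those patients can be in the trial: the exclusion criterion in protocol 4.2 reads "INR >1.2 unless patient is on anticoagulant therapy".

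**AESI classification.** SAP 10.7.7 begins "An AE will be classified as an AESI is the question" (the second *is* is plainly a slip for *if*) and makes the CRF answer the sole criterion. Protocol 7.1.5 also has the investigator mark the eCRF, but against stated definitions. The anemia definition is CTCAE Grade ≥2 anemia together with "absolute reticulocyte counts of <50% of the Baseline value, which is confirmed by repeat testing". The hypothyroidism definition is TSH ≥10 mIU/L with reduced free T4, repeated at the central laboratory.

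**Related outputs.** SAP 12.6.2 summarizes and lists adjudicated events, including DILI, anemia and hypothyroidism. Under SAP 12.6.3, hematology gets shift tables to the worst CTCAE grade, and "thyroid function will be summarized descriptively by scheduled visit using the SS". SAP 6.1, which lists changes from the protocol, does not mention the INR exception.

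**The concern.** The INR row is an error of content. An anticoagulated patient has a raised INR for a reason unrelated to liver injury, which is why the protocol sets the criterion aside for them at eligibility, at retest and at the stopping rules. Counting them in a by-arm liver-safety table adds false positives.

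The excess need not fall evenly across arms. Randomization is stratified only by ALP, so chance imbalance is possible. Protocol 6.7 also lists warfarin among the drugs needing caution because setanaxib weakly inhibits CYP2C9, so an interaction could raise INR in the active arms without any liver injury.

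The AESI point is about checkability. The anemia AESI is aimed at a marrow signal seen in dogs, where one animal's reticulocyte count fell by about 90% (protocol 1.1.3). Anemia is also a complication of PBC itself (protocol 1.1.1.1). A count of Grade ≥2 anemia alone therefore does not separate marrow suppression from other causes; the reticulocyte pairing does. For hypothyroidism, no planned table counts TSH ≥10 mIU/L. A reader who wanted to check the ticked AESI counts against the definitions would have to work through listings.

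**Working it through.** **1. The INR criterion, side by side**

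| Place | INR criterion | Anticoagulated patients |
|---|---|---|
| Protocol 4.2, exclusion 7 | >1.2 excludes | exempt, so eligible |
| Protocol 5.3.2.1, retest trigger | >1.5 | exempt |
| Protocol Appendix II, criteria A, B and C | >1.5 | exempt each time it appears |
| SAP 12.6.3, sDILI table and listing flag | >1.5 | counted |

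**2. Size of the INR error**

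The inputs are the planned enrolment of 60 to 70 with a target of 66, and 1:1:1 allocation. Arms are then 60/3 = 20, 66/3 = 22 and 70/3 = 23.3. Each wrongly counted patient adds 100/n percentage points:

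- n = 20: 100/20 = 5.0
- n = 22: 100/22 = 4.5
- n = 23.3: 100/23.3 = 4.3

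The number of anticoagulated patients with INR >1.5 is not given. If it is assumed to be 0 to 2 per arm, the excess at n = 22 is 0 to 2/22 = 9.1 points.

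**3. Would the exception lose a protocol-defined case?**

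No. Every use of INR in criteria A, B and C carries the same exception, so a patient removed from the row could not have met the protocol through INR. The other rows still catch the remaining laboratory-only routes. ALT or AST >3× or >5×Baseline implies >2×Baseline, and >10×ULN implies ≥3×ULN. Bilirubin >2×ULN has its own row. Routes that depend on symptoms are outside any laboratory table.

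**4. Where could the paired AESI definitions appear?**

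- AESI tables (SAP 12.6.1): these use the CRF tick.
- Adjudicated-event summary (SAP 12.6.2): this covers anemia and hypothyroidism. Definitions are left to an Adjudication Charter that is not among the documents. The SAP describes the set as events requiring interruption of study drug. That is broader than the AESI, because Grade ≥2 anemia alone (protocol 5.3.2.2) or TSH ≥10 mIU/L alone (5.3.2.3) requires interruption.
- Hematology shift tables: one parameter at a time.
- Hematology change from Baseline (protocol 8.4.2): reticulocytes are summarized, but not jointly with anemia grade.
- Thyroid function: by-visit descriptive summaries and out-of-range counts, with no count at 10 mIU/L and no pairing with free T4.

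So, adjudication apart, no planned table derives either pair from laboratory values.

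**5. ALT/AST baseline**

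Protocol 5.3.2.1 has it "determined by averaging the values obtained at Screening and Baseline/Day 1 to determine the arithmetic mean". SAP 10.1.1 has it "determined by the geometric mean of the last (up to) 3 measurements preceding the first administration of study drug". For two values differing r-fold, geometric mean divided by arithmetic mean is 2√r/(1+r). The SAP threshold is lower by 1 minus that ratio:

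- r = 1.2: 1 − 0.996 = 0.4%
- r = 1.5: 1 − 0.980 = 2.0%
- r = 2: 1 − 0.943 = 5.7%

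The r values are assumptions. With two values the SAP row can only be more inclusive. With a third, unscheduled value the direction can reverse: Screening 40, unscheduled 80 and Day 1 80 give (40×80×80)^(1/3) = 63.5, against an arithmetic mean of Screening and Day 1 of 60.

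**The case against.** **On INR:** the table is a deliberately wide screen, affected patients are flagged in listings, and medications are listed by patient, so a careful reader could undo the miscount. That limits the harm. It does not make the row right, because a by-arm proportion is read as it stands.

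**On AESIs:** a reader might infer that AESIs are counted from the tick alone, that no planned output applies the definitions, or that cases will be missed. The documents do not support any of these.

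- The tick is the protocol's own procedure.
- A blinded committee adjudicates AESIs, and its results are summarized. Since the Charter is not available, nobody can say from these documents that it does not apply the paired definitions.
- Interruption is mandatory at Grade ≥2 anemia and at TSH ≥10 mIU/L, and laboratory abnormalities that lead to interruption must be recorded as AEs (protocol 7.1.4).
- Protocol 10.2 provides computerized and manual discrepancy checks. Missing reconciliation in the SAP does not show that none is planned.

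What remains is narrower. Under protocol 7.1.5 adjudication starts from the same investigator entry, so it is not an independent check on an unticked case. SAP 12.4 shows that entry gaps did occur in this trial, since unentered deviations had to be derived by program, although that concerned deviations and not safety events.

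**On baseline:** a reader might call the geometric mean a breach of the protocol. The arithmetic mean sits in the rules for investigator management. Protocol 8.1 lets the SAP set baselines for endpoints other than the primary, and SAP 10.1.1 does so. That objection stands.

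**Conclusion.** The INR row is wrong as written. It contradicts protocol 5.3.2.1 and Appendix II for patients whom protocol 4.2 admits, and SAP 6.1 does not declare the change. The size is 4.3 to 5.0 percentage points per affected patient, depending on arm size. The total rests on the number of anticoagulated patients with INR >1.5, which the documents do not give and which could be zero. AESI counts are not affected, because they do not come from this table.

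The missing laboratory cross-check for the paired anemia and hypothyroidism definitions is a secondary, worthwhile improvement, not a failure of safety reporting. No misclassification rate can be derived, and outright omission of a case is unlikely. The ALT/AST baseline is a minor consistency point: about 0.4% to 2% on the threshold if pre-dose values differ 1.2- to 1.5-fold.

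**What to change.** **Correct:** in SAP 12.6.3, apply the anticoagulant exception to the INR row and to the matching listing flag. Identify anticoagulants from the ATC-coded concomitant medications (SAP 12.3.2), with use judged at the date of the INR sample and the drug list fixed while blinded. A footnote giving the number of exempted patients with INR >1.5 by arm keeps the information visible. The cost is very small.

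**Add, if agreed:** keep the ticked and adjudicated AESI tables. Beside them, add by-arm flags from central-laboratory data, using all post-baseline samples including unscheduled retests. One flag is for Grade ≥2 anemia with reticulocytes below 50% of Baseline; the other is for TSH ≥10 mIU/L with reduced free T4. List every patient whose flag disagrees with the tick or the adjudication result.

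This needs modest programming on data already planned and no new visits. The downsides are a second count beside the first and some indeterminate cases. Those are mainly anemia cases whose retest was done locally, since protocol 5.3.2 keeps local results out of the eCRF. Few thyroid cases should be affected, because the definition requires a central-laboratory repeat.

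**Note:** a footnote to the sDILI table stating which ALT/AST baseline is used is enough.
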